9.4 Safety

Planned time points for all safety assessments are listed in the Schedule of Activities.

9.4.1 Physical Examinations

Refer to the Schedule of Activities for timing of assessments in [Section 2](#).

9.4.2 Vital Signs

Refer to the Schedule of Activities for timing of assessments in [Section 2](#).

9.4.3 Electrocardiograms

Refer to the Schedule of Activities for timing of assessments in [Section 2](#).

For the purposes of monitoring participant safety, investigators will review 12-lead ECGs per the protocol-specified schedule as outlined in time and events tables (see [Section 2](#)) using their site's standard ECG machines.

9.4.4 Clinical Safety Laboratory Assessments

Investigators must document their review of each laboratory safety report.

A local laboratory will perform the analyses and will provide reference ranges for these tests. Results of clinical laboratory tests performed up to Day -1 must be available prior to dosing.

The laboratory tests that will be performed for study participants are shown in [Table 9.4.4-1](#).

Results of all laboratory tests required by this protocol must be provided to BMS, either recorded on the laboratory pages of the CRF or by another mechanism as agreed upon between the investigator and BMS (eg, provided electronically). If the units of a test result differ from those printed on the CRF, the recorded laboratory values must specify the correct units. Any abnormal laboratory test result considered clinically significant by the investigator must be recorded on the appropriate AE page of the CRF.

Table 9.4.4-1: Laboratory Assessments

Hematology

Hemoglobin
Hematocrit
Total leukocyte count, including differential
Platelet count

Serum Chemistry

Aspartate aminotransferase	Total Protein
Alanine aminotransferase	Albumin
Total bilirubin	Sodium
Direct bilirubin	Potassium
Alkaline phosphatase	Chloride
Lactate dehydrogenase	Total serum calcium
Creatinine	Phosphorus
Blood urea nitrogen	Magnesium
Uric acid	Creatinine clearance- screening only
Glucose (Fasting at screening only)	Bicarbonate/Carbon dioxide
Amylase	Ferritin
Lipase	PTT/PT
HDL, LDL	
Gamma-glutamyl transferase only when alkaline phosphatase increases to Grade ≥ 2 .	

Urinalysis

Protein
Glucose
Blood
Leukocyte esterase
Specific gravity
pH
Microscopic examination (performed if blood, protein, or leukocyte esterase is present on dipstick)

Serology

Serum for hepatitis C antibody (if hepatitis C antibody is positive reflex to hepatitis C RNA) or hepatitis C RNA, hepatitis B surface antigen; HPV status; and HIV-1 and HIV-2 antibody. (Testing for HIV-1, HIV-2 must be performed at sites where mandated by local requirements)

Other Analyses

Serum or urine pregnancy test (WOCBP only)
TSH with reflex testing to free T3 and free T4 if TSH is abnormal.
FSH (if needed to document postmenopausal status)

9.4.5 Suicidal Risk Monitoring

Not applicable.

9.4.6 Imaging Safety Assessment

Any incidental findings of potential clinical relevance that are not directly associated with the objectives of the protocol should be evaluated and handled by the study investigator as per standard medical/clinical judgment.

9.5 Pharmacokinetic

9.5.1 Pharmacokinetic Assessment Following BMS-986242 Monotherapy

The PK of BMS-986242 and its metabolites (if applicable) will be derived from plasma concentration versus time and urinary excretion data. Individual participant PK parameter values will be derived by noncompartmental methods by a validated PK analysis program. Actual times will be used for the analyses.

The PK parameters to be assessed for BMS-986242 and selected metabolites following single-dose administration in Cycle 00 and multiple-dose administration in Cycle 0 include but are not limited to:

C _{max}	Maximum observed plasma concentration
T _{max}	Time of maximum observed plasma concentration
AUC(0-T)	Area under the concentration-time curve from 0 to last observed collection time (clinical pharmacology substudy)
AUC(INF)	Area under the concentration-time curve from 0 extrapolated to infinity time (clinical pharmacology substudy only)
AUC(TAU)	Area under the concentration-time curve in 1 dosing interval
C _{trough}	Trough observed plasma concentration at the end of the dosing interval
CLT/F	Apparent total body clearance
V _{ss} /F	Apparent volume of distribution at steady-state
T-HALF	Apparent terminal phase half-life
AI	Accumulation index, calculated based on ratio of AUC and C _{max} at steady state to after the first dose
%UR24	Percent urinary recovery over 24 hours
%UR72	Percent urinary recovery over 72 hours (clinical pharmacology substudy only)

In addition, the following PK parameters for select BMS-986242 metabolites may also be assessed if data permit:

MR_C _{max}	Ratio of metabolite C _{max} to parent C _{max} , corrected for molecular weight
MR_AUC(TAU)	Ratio of metabolite AUC(TAU) to parent AUC(TAU), corrected for molecular weight
MR_AUC(0-T)	Ratio of metabolite AUC(0-T) to parent AUC(0-T), corrected for molecular weight (clinical pharmacology substudy only)
MR_AUC(INF)	Ratio of metabolite AUC(INF) to parent AUC(INF), corrected for molecular weight (clinical pharmacology substudy only)

9.5.2 Pharmacokinetic Assessment Following Combination Treatment with BMS-986242 and Nivolumab

Plasma samples for BMS-986242 will be collected for all participants receiving combination treatment with BMS-986242 and nivolumab. Plasma concentration data will be tabulated using summary statistics. These data, together with data from the monotherapy, may also be pooled with other datasets for PPK analysis, which will be presented in a separate report.

Serum samples for nivolumab PK and immunogenicity assessments will be collected for all participants receiving combination treatment of BMS-986242 and nivolumab. End-of-infusion and trough concentrations will be tabulated using summary statistics. These data may also be pooled with other datasets for PPK analysis, which will be presented in a separate report.

9.5.3 Pharmacokinetics: Collection and Processing

Detailed sampling schedules to be followed for the assessment of PK and immunogenicity for all analytes in the study are provided in [Table 9.5.3-1](#). All time points are relative to the start of BMS-986242 dosing. Predose samples should be taken within 30 minutes before the start of BMS-986242 administration. Nivolumab end-of-infusion samples should be taken just prior to the end of infusion (preferably within 2 minutes). Further details of sample collection, processing, and shipment will be provided in the laboratory procedures manual. On-treatment PK samples are intended to be drawn relative to actual dosing days; if a dose occurs on a different day within the cycle due to delays or minor schedule adjustments, PK samples should be adjusted accordingly.

[Table 9.5.3-2](#) lists the PK sampling and ECG collection schedules to be followed for the clinical pharmacology substudy (Cycle 00). Serial ECGs (reviewed by a core laboratory) will be collected with matching PK samples. Twelve-lead continuous ECG (Holter) will be used in the QTc substudy. Each ECG time point will be collected in triplicates. ECGs should be performed after the participant has been resting supine for at least 10 minutes and should be completed prior to any PK/pharmacodynamic sample blood collections when assessments occur at the same time points. All serial ECGs will be transmitted to a central laboratory for measurement of intervals and classification of ECG abnormalities. At the end of the clinical pharmacology substudy, participants will follow PK collection schedule after BMS-986242 + nivolumab combination treatment provided in [Table 9.5.3-1](#).

Table 9.5.3-1: Pharmacokinetic, Anti-drug Antibody (ADA/Immunogenicity) Sampling Schedule for BMS-986242 and Nivolumab (Dose Escalation Part 1 and Dose-Expansion Cohorts Part 2)

Study Day of Sample Collection	Event	Time (Relative To BMS-986242 Dosing) Hour:Min	BMS-986242 and Metabolites Plasma Sample	BMS-986242 Plasma Sample (Biotransformation)	BMS-986242 and Metabolites Urine Sample	Nivolumab Serum Sample	Nivolumab ADA Sample
C0D1	Predose	00:00					
		01:00	X		X (0-8 h)		
		02:00	X				
		03:00	X				
		04:00	X				
		06:00	X				
		08:00	X				
C0D2	Predose	00:00	X		X (8-24 h)		
C0D8	Predose	00:00	X				
C0D14	Predose	00:00	X	X			
		01:00	X	X			
		02:00	X	X			
		03:00	X	X			
		04:00	X	X			
		06:00	X	X			
		08:00	X	X			
C0D15	Predose ^a		X	X			
C1D1	Predose	00:00	X	X		X	X

Table 9.5.3-1: Pharmacokinetic, Anti-drug Antibody (ADA/Immunogenicity) Sampling Schedule for BMS-986242 and Nivolumab (Dose Escalation Part 1 and Dose-Expansion Cohorts Part 2)

Study Day of Sample Collection	Event	Time (Relative To BMS-986242 Dosing) Hour:Min	BMS-986242 and Metabolites Plasma Sample	BMS-986242 Plasma Sample (Biotransformation)	BMS-986242 and Metabolites Urine Sample	Nivolumab Serum Sample	Nivolumab ADA Sample
	EOI ^b	01:00	X			X	
		02:00	X				
		04:00	X				
C3D1	Predose	00:00	X			X	X
	EOI	01:00	X			X	
Every 4 Cycles from C5D1	Predose	00:00	X			X	X
EOT			X			X	X
FUC ^c			X			X	X

Note: Each treatment cycle is 4 weeks (except Cycle 0).

Abbreviations: ADA = anti-drug antibody; EOI = end of infusion; FU = follow-up.

^a This sample should be taken 24 hours after the previous BMS-986242 dose on Cycle 0 Day 14 if Cycle 1 Day 1 does not occur on the next day after Cycle 0 Day 14.

^b This sample should be taken preferably within 2 minutes prior to the end of infusion. If the end of infusion is delayed to beyond the nominal infusion duration, the collection of this sample should also be delayed accordingly.

^c Performed at the first 2 follow-up visits (up to 100 days from the EOT visit) EXCEPT for participants who have WITHDRAWN CONSENT.

Table 9.5.3-2: Pharmacokinetic Sampling and ECG Collection Schedule for BMS-986242 in the Clinical Pharmacology Substudy

Study Day of Sample Collection	Event	Time (Relative to BMS-986242 Dose) Hour: Min	BMS-986242 and Metabolites Plasma Sample	BMS-986242 and Metabolites Urine Sample	ECG
C00D1	Predose	-01:00			X
C00D1	Predose	-00:45			X
C00D1	Predose	-00:30			X
C00D1	Predose	00:00			
		01:00	X	X (0-8 h)	
		01:45			X
		02:00	X		
		02:45			X
		03:00	X		
		03:45			X
		04:00	X		
		06:00	X		
		08:00	X		
C00D2		24:00	X		X (8-24 h)
C00D3		48:00	X	X (24-48 h)	
C00D4		72:00	X	X (48-72 h)	

Table 9.5.3-2: Pharmacokinetic Sampling and ECG Collection Schedule for BMS-986242 in the Clinical Pharmacology Substudy

Study Day of Sample Collection	Event	Time (Relative to BMS-986242 Dose) Hour: Min	BMS-986242 and Metabolites Plasma Sample	BMS-986242 and Metabolites Urine Sample	ECG
C00D8 ^{a,b}	Predose	00:00 ^b	X	X	
		01:00	X	X (0-8 h)	
		02:00	X		
		03:00	X		
		04:00	X		
		06:00	X		
		08:00	X		
C00D9 ^a		24:00	X	X (8-24 h)	
C00D10 ^a		48:00 ^c	X		

Abbreviations: ADA = anti-drug antibody; EOT = end of treatment; FU = follow-up.

^a Exploratory food effect cohort only.

^b For participants not in the Food Effect cohort, C00D8 predose samples should be taken approximately 168 hours after dosing on Cycle 00 Day 1 if Cycle 1 Day 1 does not occur on the next day after Cycle 00 Day 7.

^c For participants in the Food Effect cohort, this sample should be taken 48 hours after dosing on Cycle 00 Day 8 if Cycle 1 Day 1 does not occur on the next day of Cycle 00 Day 9.

9.5.4 Pharmacokinetic Sample Analyses

The plasma and urine samples of BMS-986242 and select metabolites will be analyzed by validated liquid chromatography-mass spectrometry (LC-MS) assays, and serum samples of nivolumab and anti-nivolumab antibody will be analyzed by validated immunoassays. In addition, plasma samples will be archived for potential additional metabolite and biotransformation analysis if the need arises and to the extent possible.

9.6 Pharmacodynamics

Details on biomarker sampling and analysis are provided in Section 9.8.

9.7 Pharmacogenomics

Details on biomarker sampling and analysis are provided in Section 9.8.

9.7.1 Absorption, Distribution, Metabolism, and Excretion Sampling

A 6-mL whole blood sample will be drawn at baseline (Cycle 0 Day 1) for potential analysis of deoxyribonucleic acid (DNA) variants in absorption, distribution, metabolism, and excretion (ADME)-related genes (see list of ADME-related genes from <http://pharmaadme.org>). Further details of blood collection and processing will be provided to the site in the procedure manual.

Details on biomarker sampling and analysis are provided in Section 9.8, [Table 9.8-1](#), and [Table 9.8-2](#).

9.9 Health Economics OR Medical Resource Utilization and Health Economics

Health Economics/Medical Resource Utilization and Health Economics parameters will not be evaluated in this study.

10 STATISTICAL CONSIDERATIONS

10.1 Sample Size Determination

10.1.1 Dose Escalation

During the dose-escalation trial, the sample size at each dose in these arms depends on observed toxicity and posterior inference.

Up to approximately 78 participants are planned to be enrolled for Part 1 (dose escalation) and clinical pharmacology substudy: approximately 30 participants for the dose-escalation phase, with up to 24 additional participants in Part 1 for additional characterization of the safety, PK, and pharmacodynamic profile of BMS-986242, and approximately 24 participants for the clinical pharmacology substudy (including food effect). [Appendix 7](#) provides additional details for the operating characteristics of the BLRM for monotherapy and BLRM-copula for combination therapy based on doses from 25 mg; an addition of 12.5 mg is expected to provide similar operating characteristics..

For the food effect assessment, the sample size is not based on statistical power for comparison but on consideration of the precision of the estimates of geometric means of C_{max} and AUC(0-T) of BMS-986242.

For a sample size of 6 participants, there is an 80% probability for the 90% confidence interval to be within 79.6% to 125.7% of the point estimate of the geometric mean for C_{max} and within 80.4% to 124.4% of the point estimate of the geometric mean for AUC(0-T). This calculation assumes that log(C_{max}) and log(AUC[0-T]) of BMS-986242 are normally distributed with a standard deviation (SD) of 0.23 and 0.22, respectively, as estimated from a study of a related compound.

10.1.2 Dose-expansion Cohort

Dose-expansion cohorts of BMS-986242 administered in combination with nivolumab in 6 disease-restricted populations will be included. These are melanoma, NSCLC, SCCHN, RCC, bladder, and gastric cancer, with separate cohorts based on prior PD-(L)1 exposure in 5 of the tumor types (except gastric cancer). Approximately 20 participants will be included for each dose-expansion cohort, for a total of 220 participants for Part 2. The sample size of 20 participants per dose-expansion cohort is not based on statistical power for comparison but on consideration of the precision of the estimates for ORR proportion. A total of 20 participants are expected to provide a standard error of the estimate of 7% to 11% for ORR proportions between 10% and 50%.

10.2 Populations for Analyses

For purposes of analysis, the following populations are defined as follows:

Population	Description
Enrolled	All participants who sign informed consent and are registered into the IRT
Treated	All participants who received at least 1 dose of study treatment
Pharmacokinetic	All treated participants who have available concentration-time data from the participants who received any BMS-986242 or nivolumab
Immunogenicity	All treated participants who have received nivolumab and have a baseline and at least 1 post-treatment immunogenicity measurement
Biomarker	All treated participants who have available biomarker data

Note: Analyses of safety, extent of exposure, biomarkers, PK, efficacy, and pharmacodynamics will be based on the treated population.

10.3 Statistical Analyses

The statistical analysis plan will be developed and finalized before database lock. Below is a summary of planned statistical analyses of the primary and secondary endpoints.

10.3.1 Efficacy Analyses

Listings of participant efficacy will be provided. The following efficacy analyses may be performed on the treated population for the final analysis, if appropriate (Table 10.3.1-1). Details on censoring scheme on time-to-event endpoints such as DOR for each tumor type, progression-free survival, and overall survival will be described in the statistical analysis plan.

Table 10.3.1-1: Efficacy - Statistical Analyses

Endpoint	Statistical Analysis Methods
ORR BOR for a participant will be assessed per RECIST v1.1 for solid tumors by investigator	Estimate of ORR and corresponding 2-sided exact 95% exact CI by the Clopper-Pearson method by treatment.
Median DOR DOR for a participant with a BOR of CR or PR, defined as the time between the date of first response and the date of the first objectively documented disease progression (per RECIST v1.1) or death, whichever occurs first	Median DOR using the Kaplan-Meier method and corresponding 2-sided 95% CI using Brookmeyer and Crowley methodology (using log-log transformation) by treatment
PFSR at 6, 9, 12, and 24 months PFS for a participant is defined as the time from the first dosing date to the date of first objectively documented disease progression or death due to any cause, whichever occurs first	Estimate by the Kaplan-Meier method and corresponding 95% CI will be derived based on Greenwood formula by treatment
OSR at 6, 12, and 24 months (after the last dose of study treatment) OS for a participant is defined as the time from date of first dose of study treatment to the date of death from any cause	Estimate by the Kaplan-Meier method and corresponding 2-sided 95% CI will be derived based on Greenwood formula by treatment

Note: ORR/DOR analysis may not be performed in case there are too few responses.

Abbreviations: BOR = best overall response; OS = overall survival.

10.3.2 Safety Analyses

The safety analyses will be performed on the treated population for the final analysis (Table 10.3.2-1).

Table 10.3.2-1: Safety - Statistical Analyses

Endpoint	Statistical Analysis Methods
Incidence of DLTs, AEs, SAEs, AEs leading to discontinuation and deaths	DLT rate by dose level, frequency distribution of treated participants with AE using the worst CTC grade. Participants will only be counted (1) once at the PT level, (2) once at the system organ class level, and (3) once in the 'total participant' row at their worst CTC grade, regardless of system organ class or PT. AEs will be graded according to CTCAE v4.03 and coded using the latest version of MedDRA
Laboratory abnormalities	Laboratory shift table using the worst CTC grade on treatment per participant Laboratory values will be graded according to CTCAE v4.03
Changes from baseline in laboratory parameters, vital signs, and ECG	Summary statistics for timepoint and change from baseline by time and dose.
Summary measures of parameters from posterior distribution of the dose-DLT profile	Summary statistics for posterior distribution parameters and plot of final dose-DLT curve

Abbreviations: MedDRA = Medical Dictionary for Regulatory Activities; PT = preferred term.

Additional exposure response analyses will be performed for QTc during the clinical pharmacological substudy.

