4 OBJECTIVES AND ENDPOINTS

The objective and endpoints for this study are shown in [Table 4-1](#).

Table 4-1: Objectives and Endpoints

Objectives	Endpoints
Primary	

 Part 1: Dose Escalation To determine the safety, tolerability, DLTs, and MTD/MAD/alternative dose of BMS-986242 administered as monotherapy (lead-in cycle) and in combination with nivolumab in participants with advanced malignant tumors Part 2: Dose-Expansion Cohort(s) To evaluate the safety and tolerability of BMS-986242 in combination with nivolumab in participants with advanced malignant tumors 	
 Incidence of DLTs, AEs, SAEs, AEs leading to discontinuation, deaths, and clinical laboratory test abnormalities Additional safety endpoints include changes from baseline in laboratory parameters, vital signs, and ECGs.
Secondary	

 To characterize the PK of BMS-986242 administered alone and in combination with nivolumab To characterize the pharmacodynamic activity of BMS-986242 administered alone and in combination with nivolumab To characterize the immunogenicity of nivolumab when administered in combination with BMS-986242 To assess the preliminary anti-tumor activity of BMS-986242 administered in combination with nivolumab in advanced malignant tumors 	
 Summary measures of selected BMS-986242 PK parameters, such as Cmax, Tmax, AUC(TAU), AUC(INF), Ctrough, T-HALF, CLT/F, Vss/F, AI, %UR24, %UR72, and exposure ratios of select BMS-986242 metabolites to BMS-986242 from concentration-time data during BMS-986242 monotherapy and BMS-986242 Ctrough during combination treatment Summary measures of change from baseline (and/or percent change) for serum and tumor kynurenine and related metabolites Incidence of ADA to nivolumab in combination with BMS-986242 ORR in participants with a BOR of CR or PR per RECIST version 1.1 for solid tumors; mDOR, and PFSR at 6, 9, 12, and 24 months

[REDACTED]
 
[REDACTED]
 
[REDACTED]
 
[REDACTED]
 
[REDACTED]
	
[REDACTED]
 
[REDACTED]
 
[REDACTED]
 
[REDACTED]
 
[REDACTED]

Table 4-1: Objectives and Endpoints

Objectives	Endpoints

[REDACTED]
	
[REDACTED]

Abbreviations: %UR24 = percent urinary recovery over 24 hours; %UR72 = percent urinary recovery over 72 hours

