Cohort tolerability assessment and subsequent dose recommendation may occur when 2 DLT-evaluable participants within a cohort have completed the 6-week DLT observation period (see [Section 7.4.1](#) for criteria for DLTs). DLTs occurring within the 2-week lead-in period (DLT observation period for monotherapy) will be used to fit the BLRM model for monotherapy. DLTs occurring within the 4 weeks of combination period (DLT observation period for combination) will be used to fit the BLRM-copula model. If a potential DLT occurring in any third evaluable participant does not influence the dose recommendation by BLRM (-copula), then the BLRM (-copula)-recommended next dose level may proceed without waiting for the third participant to complete the corresponding DLT observation period after discussion and agreement by the sponsor and investigators. The lower recommended dose from both models will be considered for the next dose escalation. Participants receiving $\geq 75\%$ (11 out of 14 doses) of BMS-986242 in the 2-week lead-in cycle will be considered as DLT-evaluable participants for BMS-986242 monotherapy. Participants who receive at least 1 dose of nivolumab and have been followed at least 5 days and receive $\geq 75\%$ BMS-986242 (21 out of 28 doses) in the 4-week DLT observation period for combination therapy will be considered as DLT-evaluable participants. Continuous re-assessment of dose recommendation by BLRM will be carried out at each dose level after each cohort of participants with consideration of all available DLT information. In order to allow additional safety, PK, and pharmacodynamic assessment, in Part 1 up to 12 additional participants may be enrolled at any dose level at or below the MTD, up to a total of 24 additional participants.

No intra-participant dose escalation is allowed, although dose modifications of BMS-986242 may be permitted (see [Table 7.4.2-1](#)).

[figure not shown]
Sentinel Participant: During dose escalation, a staggered dosing (sentinel participant) approach will be used. In the first dose level, the first participant in both lead-in and combination will receive the Cycle 0 Day 1 or Cycle 1 Day 1 dose(s) of study treatment(s) and be observed for 5 days before additional participants in that cohort receive monotherapy or combination study treatment. In subsequent dose levels, a sentinel participant with a 5 day observation period will be used for Cycle 0 Day 1.

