7.2 Method of Treatment Assignment

During the screening visit, the investigative site will call into the enrollment option of the IRT designated by BMS for assignment of a 5-digit participant number that will be unique across all sites. Enrolled participants, including those not dosed, will be assigned sequential participant numbers starting with 00001 (eg, 00001, 00002, 00003... 00010). The participant identification number will ultimately be composed of the site number and participant number. For example, the first participant screened (ie, enrolled) at site number 1 will have a participant identification number of 0001 00001. Once it is determined that the participant meets the eligibility criteria following the screening visit, the investigator site will call the IRT within 3 days prior to the first study treatment administration for the participant to be assigned to a treatment group.

During dose escalation, participants who are not evaluable for DLT determination may be replaced. Replacement participants will be assigned to the same treatment but will be assigned a new participant number.

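### The DLT rate is assigned to the treated population and no DLT-evaluable population is defined, so participants lost without a DLT pull the reported primary rate down

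*Combined protocol and SAP*

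**What the plan says.** **Endpoint.** Section 4 (Table 4-1) gives the primary endpoint as "Incidence of DLTs, AEs, SAEs, AEs leading to discontinuation, deaths, and clinical laboratory test abnormalities".

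**Analysis population.** Section 10.3.2 states: "The safety analyses will be performed on the treated population for the final analysis". Table 10.3.2-1 gives the method for the DLT and adverse event row as "DLT rate by dose level, frequency distribution of treated participants with AE using the worst CTC grade", with no separate denominator for the DLT rate. Section 10.2 adds: "Note: Analyses of safety, extent of exposure, biomarkers, PK, efficacy, and pharmacodynamics will be based on the treated population". It defines treated as "All participants who received at least 1 dose of study treatment". The other populations listed are Enrolled, Pharmacokinetic, Immunogenicity and Biomarker; none is DLT-evaluable.

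**Evaluability.** Section 5.1.2.1 defines it for each window. For the lead-in, those receiving at least 75% (11 of 14 doses) "of BMS-986242 in the 2-week lead-in cycle will be considered as DLT-evaluable participants for BMS-986242 monotherapy". For the combination it asks for one nivolumab dose, at least 5 days of follow-up and at least 75% (21 of 28) of BMS-986242 doses. Section 7.4.1 instead asks for at least 21 days of observation after the first combination dose.

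**Replacement.** Section 7.2 says that, during escalation, "participants who are not evaluable for DLT determination may be replaced". Section 7.4.1 allows replacement at the same dose level after withdrawal for a reason other than a DLT. Section 5.1.2.1 foresees extra enrolment to secure at least 3 evaluable participants per dose level.

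**The concern.** A participant who leaves the DLT window early without a DLT has not been shown to be free of one. Such participants are replaced for that reason. If they stay in the denominator, they are counted as if they had completed the window without a DLT. The replacement is counted as well.

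There are also two windows, 2 weeks of monotherapy and 4 weeks of combination, feeding two models. A participant who stops in Cycle 0 is treated at that dose level but never enters the combination window. On a treated denominator that participant still counts towards the combination rate.

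At stake is the reported value of a primary endpoint, in cohorts that start at about 4 participants and against limits of 16% and 33% (Appendix 7, Section 3). Table 10.3.2-1 would also show a crude rate on one set of participants beside a posterior dose-DLT curve fitted to another.

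**Working it through.** **Inputs.** Evaluability cut-offs and cohort sizes come from Section 5.1.2.1, toxicity categories from Appendix 7, Section 3, and the treated denominator from Sections 10.2 and 10.3.2. The number of non-evaluable participants is not given. I assume 1 to 3 per dose level or, as a share, 5% to 30% of those treated, none with a DLT.

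**The plan's own figures.** No sample size or stated DLT rate depends on this denominator, so there is no planned result to reproduce. The reference figures check: 1/6 = 16.7% (plan: about 16%), 2/6 = 33.3% (plan: about 33%), 11/14 = 78.6% and 21/28 = 75.0%.

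**Formula.** Let x be the DLTs, n the evaluable participants and k the treated participants lost without a DLT.

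- Evaluable rate = x/n
- Treated rate = x/(n + k) = (x/n) × (1 − r), where r = k/(n + k)

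For x > 0 and k > 0 the treated rate is always the lower of the two.

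| DLTs / evaluable | Evaluable rate | k = 1 | k = 2 | k = 3 |
|---|---|---|---|---|
| 1/3 | 33.3% | 25.0% | 20.0% | 16.7% |
| 1/6 | 16.7% | 14.3% | 12.5% | 11.1% |
| 2/6 | 33.3% | 28.6% | 25.0% | 22.2% |
| 3/9 | 33.3% | 30.0% | 27.3% | 25.0% |
| 4/12 | 33.3% | 30.8% | 28.6% | 26.7% |

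One lost participant moves 2/6 from above to below 33%, and 1/6 from above to below 16%.

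**By share.** A 40% evaluable rate is reported as 38.0%, 36.0%, 32.0% or 28.0% when r is 5%, 10%, 20% or 30%. It falls below 33% once r exceeds 1 − 33/40 = 17.5%.

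**Combination window.** Suppose 7 participants are treated at a dose, 1 stops in Cycle 0, and 2 of the 6 who go on have a DLT in the combination window. The rate among those at risk is 2/6 = 33.3%; on treated participants it is 2/7 = 28.6%. This holds even if the Cycle 0 stop was itself a lead-in DLT, because that event belongs to the other window.

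**Can the evaluability rule be used unchanged?** Section 5.1.2.1 rests on the share of doses received and states no exception for a participant with a DLT. Section 7.4.3 requires treatment to be held after a DLT. A DLT on lead-in day 5 with no further dosing leaves at most 5/14 = 35.7% of doses, below 75%. Read literally, that case would leave both numerator and denominator, which would also lower the rate.

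**The case against.** The strongest reply is that the denominator is inferred. The DLT phrase in Table 10.3.2-1 names none; the word treated there attaches to the adverse event distribution. The treated assignment comes from a general sentence and a note. Read literally, it would even sweep in Part 2 participants at the same dose, which suggests it was not written with the DLT rate in mind. The sponsor's own nivolumab data in Appendix 7, Table 2 are DLTs over evaluable participants. Section 10.3 calls itself a summary and points to a SAP still to be finalized.

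This lowers the certainty about intent, but the point remains. Treated is the only population assigned, and it is assigned twice. Section 10.3.1 expressly defers censoring rules to the SAP; Section 10.3.2 defers nothing on this. In an open-label study with a SAP finalized only before database lock, the denominator could otherwise be settled with the DLT data in view.

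Three limits stand in full. Section 7.4.1.1 classes toxicity-driven under-dosing, and toxicity causing more than 2 weeks of delay, as a DLT, so dilution comes only from losses without a DLT. Replacement is optional. The size is hypothetical.

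A reader might infer that the MTD itself would be set too high, particularly because Appendix 7, Section 3 words the 33% limit on treated participants. The documents do not support that. Escalation follows the model posteriors, Sections 5.1.2.1 and 7.4.1 tie escalation decisions to evaluable participants, and the final MTD rests on the models and all available data. A reader might also infer that clinical pharmacology substudy participants, who have no 2-week lead-in, dilute the lead-in rate further. Section 7.4.1 defines the windows for Part 1 Cycle 0 and the combination, and Section 5.1.2.1 counts the substudy separately, so their inclusion is not established.

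**Conclusion.** The point holds for the reported DLT rate. As written, the plan places a primary endpoint on a population that includes participants who could not supply a complete outcome, and the resulting bias is downward. One such participant takes 2/6 = 33.3% to 28.6%, and two take it to 25.0%.

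The direction follows from the text, given at least one DLT and at least one loss without a DLT. The size rests on assumed counts. The reported rate will also disagree with the evaluable data behind the models whenever such a loss occurs. No effect on the model dose recommendations is shown.

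**What to change.** 1. Reconcile the two statements of combination evaluability first: at least 5 days of follow-up in Section 5.1.2.1 and at least 21 days in Section 7.4.1.
2. Add two DLT-evaluable populations to Section 10.2, one for the 2-week lead-in and one for the 4-week combination window, matching the data that enter the BLRM and BLRM-copula.
3. State that any participant with a DLT in a window counts as evaluable for that window, whatever doses were received.
4. In Table 10.3.2-1, base the DLT rate by dose level on these populations, by window. Show the treated-based rate as supportive.
5. List non-evaluable participants by dose level with the reason.
6. Keep the treated population for adverse events, serious adverse events, deaths and laboratory data.

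The cost is a few lines of text and slightly more analysis work, with no new data collection. Reported DLT rates may be less favourable.
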